### 6.3 Withdrawal criteria

Subjects are free to withdraw from the study at any time, without prejudice to their continued care.

Subjects should be withdrawn from the study and encouraged to come for the SFU visit (20 weeks after the last received dose) if any of the following events occur:

1. Subject withdraws his/her consent.
2. The Sponsor or a regulatory agency requests withdrawal of the subject.

Subjects should be withdrawn from all study treatment and will be asked to return for the SFU Visit (20 weeks after the last received dose) if any of the following events occur:

1. There is confirmation of a pregnancy during the study, as evidenced by a positive pregnancy test.
- 2a. Subject develops an illness that in the opinion of the Investigator would interfere with his/her continued participation if the risk of continuing participation outweighs the potential benefit.
- 3a. Subject develops erythrodermic, guttate, or pustular form of psoriasis.
4. Subject considered as having either a suspected new LTB infection or who develop active TB or nontuberculosis mycobacterium (NTMB) infection during the study (including but not limited to, conversion demonstrated by interferon-gamma release assay [IGRA] or other diagnostic means) must be immediately discontinued from study medication, an Early Withdrawal Visit must be scheduled as soon as possible, but not later than the next regular visit.

Confirmed active TB is a serious adverse event (SAE) and must be captured on an SAE Report Form and provided to the Sponsor in accordance with SAE reporting requirements. As with all SAEs, periodic follow-up reports should be completed as per protocol requirements until such time as the TB infection resolves.

Additional information on TB policies are provided in [Section 12.6.1](#).

5. Subject is noncompliant with the study procedures or medications in the opinion of the Investigator.
6. Subject uses prohibited concomitant medications, with the exception of topicals, as defined in this protocol ([Section 7.8.2](#)), that may present a risk to the safety of the subject in the opinion of the Investigator and/or the Medical Monitor.
- 8a. Subject has active suicidal ideation as indicated by a positive response (“Yes”) to Questions 4 or 5 or to the suicidal behavior questions of the “Since Last Visit” version of the self-rated Columbia Suicide Severity Rating Scale (C-SSRS). The subject should be referred immediately to a Mental Healthcare Professional and must be withdrawn from the study.
- 9a. Subjects with a HADS-D score  $\geq 15$  must be withdrawn. Any subject who develops a HADS-D score of  $>10$  during the study should be referred immediately to a Mental Healthcare Professional for further evaluation and potential withdrawal by the Investigator.
10. Subject experiences an AE as described below:
  - Any Common Terminology Criteria for Adverse Events (CTCAE) Grade 3 and above AE that is assessed as related to study drug in the opinion of the Investigator
    - If the event is deemed to be not related to study drug by the Investigator, the subject may remain in the study after approval by the Medical Monitor.
  - Any CTCAE Grade 2 event that is evaluated as related to study drug in the opinion of the Investigator, is persistent, and falls into any of the following System Organ Classes (SOCs): “Blood and lymphatic disorders,” “Cardiac disorders,” or “Vascular disorders.”
    - Persistent is defined as lasting 28 days or more, which spans at least 2 scheduled injections.
11. Subject has a clinical laboratory value meeting the following criteria:
  - CTCAE Grade 3 and above: subjects must be withdrawn regardless of relationship to study drug or duration of event.
  - CTCAE Grade 2
    - Subjects may remain in the study if the event is transient. If a subject has a Grade 2 laboratory abnormality, a retest is required within 1 to 2 weeks at a scheduled or unscheduled visit. If the repeat value is below Grade 2, the subject may receive the next scheduled study treatment. If the value on the repeat is still Grade 2 or above, a second repeat test must be performed and results made available prior to the next scheduled study treatment. If this second repeat value is still Grade 2 or above, the subject must be withdrawn.

Investigators should attempt to obtain information on subjects in the case of withdrawal or discontinuation. For subjects considered as lost to follow-up, the Investigator should make an effort (at least 1 phone call and 1 written message to the subject), and document his/her effort (date and summary of the phone call and copy of the written message in the source documents), to complete the final evaluation. All results of these evaluations and observations, together with a narrative description of the reason(s) for removing the subject, must be recorded in the source documents. The Case Report Form (CRF) must document the primary reason for withdrawal or discontinuation.

Investigators should contact the Medical Monitor, whenever possible, to discuss the withdrawal of a subject in advance.

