### **4 STUDY VARIABLES**

#### **4.1 Primary variables**

##### **4.1.1 Primary efficacy variable**

The primary endpoint of this study is change from Baseline in PASI at Week 28.

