##### Treatment Period

During the Treatment Period, subjects will be randomized 2:1 to receive the following blinded study treatment regimens:

- Treatment arm A: Bimekizumab 320mg administered sc at Baseline and Week 4, and placebo administered at Week 16
- Treatment arm B: Bimekizumab 320mg administered sc at Baseline and Weeks 4 and 16

There will be approximately 30 subjects in treatment arm A and 15 subjects in treatment arm B. Bimekizumab will be administered in the clinic at Baseline and Week 4, and at Baseline, Week 4, and Week 16 for those in treatment arm A and treatment arm B, respectively. Additional

nondosing study visits will occur at Week 2, Week 8, Week 12, Week 20, Week 24, and Week 28.

From Week 20 through Week 28, subjects who were previously PASI25 responders but subsequently relapse (defined as returning to a less than PASI25 response) will undergo the study assessments for that visit (ie, Week 20, Week 24, or Week 28) before receiving their first dose of study treatment in the extension study at Week 20, Week 24, or Week 28. Subjects eligible for the extension study must have the assessments for SFU conducted prior to entering the extension study. Subjects who have not achieved a PASI25 response at any visit prior to Week 20 will not be eligible to enter the extension study. All subjects not enrolling in the extension study will continue in PS0016 until the SFU Visit at Week 36.

Subjects withdrawing early from the study will undergo the Early Withdrawal Visit assessments (ie, Week 36) and will enter the SFU Period.

The assessments at each Treatment Period Visit are presented in [Table 5-1](#).

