#### Safety Follow-Up Period

All subjects not continuing in the extension study, including those withdrawn from study treatment, will have a SFU Visit 20 weeks after their last dose of study medication (ie, bimekizumab or placebo).

The assessments for the SFU Visit are presented in [Table 5-1](#).

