### **8.12 Early Withdrawal Visit**

Subjects withdrawing early from the study (see [Section 6.3](#)) should undergo the same assessments scheduled for the Week 36 Visit (see [Section 8.11](#)) as soon as possible after withdrawal (as an Early Withdrawal Visit) and then enter the SFU Period, completing study participation with the SFU Visit (Week 36 Visit assessments again) 20 weeks after their last dose of study medication.

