#### Latent TB

In case the evaluation by the appropriate specialist indicates a new LTBI during the study, a prophylactic TB treatment should be initiated and the subject must be withdrawn from the study.

Every related action should be discussed in advance with the Medical Monitor.

Once withdrawn from study treatment, subjects should return for the Week 36/EWD Visit, complete all Early Withdrawal Visit assessments, and complete a SFU Visit (20 weeks after the last dose of study medication).

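### After study treatment stops, no Week 28 PASI visit is named, so the primary endpoint can go uncollected and be filled by LOCF, even in Arm A once its active doses are complete

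*Protocol*

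**What the plan says.** **Endpoint and regimen.** Protocol 4.1.1: "The primary endpoint of this study is change from Baseline in PASI at Week 28". The primary objective (3.1) is the 28-week PASI course after doses at Baseline and Week 4. Arm A, which represents that regimen, receives "Bimekizumab 320mg administered sc at Baseline and Week 4, and placebo administered at Week 16" (5.1.1). The placebo is saline (7.1).

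**After treatment stops.** Section 6.3 names the SFU Visit only: such subjects should be "withdrawn from all study treatment and will be asked to return for the SFU Visit (20 weeks after the last received dose". Section 5.1.1 says the same of everyone outside the extension, "including those withdrawn from study treatment, will have a SFU Visit 20 weeks after their last dose of study medication", and 8.11 repeats it. Section 8.12 gives subjects who leave the study an Early Withdrawal Visit (EWD), "completing study participation with the SFU Visit (Week 36 Visit assessments again) 20 weeks after their last dose of study medication".

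**Stopping drug and leaving the study are not kept apart.**
- Towards leaving: criterion 8a sits in the 6.3 list of reasons to stop treatment but requires withdrawal from the study. Section 12.1.8 (pregnancy) and 12.6.1.4 (TB) do likewise. The latent TB text in 12.6.1 reads "Once withdrawn from study treatment, subjects should return for the Week 36/EWD Visit, complete all Early Withdrawal Visit assessments", followed by the SFU.
- Towards staying: 5.1.1 has all subjects not entering the extension continue to Week 36. Section 6.3.1 keeps subjects with possible liver injury in the study until their work-up ends. Section 7.8.2 has users of prohibited medication followed to the SFU after treatment stops.
- Neither group of passages lists Week 20, 24 or 28 assessments for a subject off treatment.

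**Analysis.** SAP 4.2.1.1 expects Week 28 PASI to be missing after premature discontinuation or extension entry, imputes it by LOCF, and adds observed-case summaries. SAP 4.4 maps an EWD to a scheduled visit. Protocol 14.5 instead names NRI for the primary analysis and leaves LOCF to be considered for PASI scores. NRI defines a responder status, not a change score.

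**The concern.** The trial is meant to describe what happens to PASI as drug washes out. An Arm A subject who stops after Week 4 has received exactly the regimen in the primary objective; the only injection forgone is saline. Stopping treatment does not alter that regimen, but the visit rules may end its measurement.

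After Week 16 no dose remains in either arm, yet safety laboratory tests continue and 6.3 still applies: "CTCAE Grade 3 and above: subjects must be withdrawn regardless of relationship to study drug or duration of event". If that is read as leaving the study, there is no drug left to stop and the practical effect is to end the scheduled PASI visits.

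At stake are the Week 28 value itself and the washout observations before it, in an arm of about 30.

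**Working it through.** **1. Reproduce the plan's own figure.** SFU week = last-dose week + 20. For a Week 16 dose, 16 + 20 = 36. Adding up to 4 weeks of screening, 4 + 36 = 40, the maximum duration in Protocol 5.1.2. Placebo counts as study medication for this purpose (5.1.1).

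**2. Apply the rule to earlier last doses.**
- Last dose Baseline: 0 + 20 = Week 20.
- Last dose Week 4: 4 + 20 = Week 24.

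Both precede Week 28, and visit windows do not close the gap. A Week 4 dose given 3 days late with an SFU 7 days late falls on day 168 + 3 + 7 = 178. The Week 28 window opens on day 196 - 3 = 193.

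**3. Find which visit an EWD fills.** SAP 4.4 uses the nearest scheduled visit after the last one attended. Its own example (Day 37, last visit Week 4) gives |37 - 56| = 19 days to Week 8 against |37 - 84| = 47 to Week 12, so Week 8, as the SAP states. With illustrative EWD dates, and setting aside an early SFU:

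| Last visit | EWD (week) | Mapped to | PASI visits then missing to Week 28 | Weeks carried |
|---|---|---|---|---|
| 4 | 5.3 | 8 | 12, 16, 20, 24, 28 | 20 |
| 8 | 9 | 12 | 16, 20, 24, 28 | 16 |
| 12 | 13 | 16 | 20, 24, 28 | 12 |
| 16 | 17 | 20 | 24, 28 | 8 |
| 20 | 21 | 24 | 28 | 4 |
| 24 | 25 | 28 | none | 0 |

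The last row is unaffected. In the first three rows no Week 16 dose was given, so with the last dose at Week 4 an SFU PASI exists at Week 24. The SAP does not say to which visit an early SFU belongs. If it is placed by actual time, the carry shortens to 28 - 24 = 4 weeks.

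**4. Direction.** Protocol 2.2.1 gives a subcutaneous half-life of 27.81 days (160 mg, healthy subjects). Assuming simple exponential decline from Week 4, the remaining fraction is 0.5^(7 x weeks / 27.81): 0.50 at Week 8, 0.25 at Week 12, 0.12 at Week 16, 0.03 at Week 24 and 0.015 at Week 28. A score from Weeks 8 to 16 therefore reflects much more drug than remains at Week 28.

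**5. Size, by assumption only.** The documents give no dropout rate, effect size or SD. Suppose 90% improvement is carried forward and true Week 28 improvement is 25% to 75%. The shift in the Arm A mean per subject is (carried - true)/30:
- (90 - 75)/30 = 0.5 points
- (90 - 25)/30 = 2.2 points

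Three such subjects give 1.5 to 6.5 points. On the PASI scale, with baseline 12 (the entry minimum) to 30 (assumed), three subjects shift the mean change by 3/30 x 12 x 0.15 = 0.18 to 3/30 x 30 x 0.65 = 1.95.

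**The case against.** Several points on the other side stand.

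- **Silence is not a prohibition.** Section 8.12 covers subjects leaving the study, while the 6.3 lead-in simply omits intermediate visits. A reader might infer that the protocol orders PASI visits to stop; it does not. What remains is that no section asks for them, that the SFU can fall before Week 28, and that 5.1.1 places the SFU both at Week 36 for all non-extension subjects and 20 weeks after the last dose.
- **Nothing collected is discarded.** PASI is taken at the EWD and the SFU. The Week 28 value is uncollected, not thrown away.
- **The carried score need not be near the best response.** It may be the EWD value or a Week 24 SFU value, which would reduce the overstatement.
- **The analysis is descriptive.** There is no hypothesis test, and SAP 8.1.2 adds observed-case tables and unimputed individual plots. These show the data honestly but still lack the stopped subjects at Week 28.
- **Up to 10 withdrawn subjects may be replaced (6.5).** That limits loss of information. It does not remove the imputed value, since the SAP's FAS (3.5.4) keeps any dosed subject with a Baseline PASI.

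Two further inferences are not supported. Stopping follows adverse events and laboratory values, so a reader might call the losses informative about PASI; the documents do not show this. The amendment log shows that a Week 28 return for treatment withdrawals was removed; that is history, not evidence of a current error.

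**Conclusion.** The point holds as a gap in data collection and an unreconciled distinction between stopping drug and leaving the study. The visit arithmetic is certain: with a last dose at Baseline or Week 4, the SFU Visit comes before Week 28 and no later PASI is planned. With a last dose at Week 16, Week 28 lies between the EWD and the SFU with no visit named, unless the EWD follows the Week 24 visit.

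The direction, an overstated Week 28 improvement under LOCF, is likely because drug is washing out, but it assumes that PASI worsens as exposure falls. The per-subject range in the working is conditional on the assumed 90% and 25% to 75%; no total bias can be stated. A reader might infer a definite bias from modelling plausible dropout, but any such figure would come from invented rates. Subjects who relapse into the extension at Week 20 or 24 also lack Week 28 data; that is a separate route which this point does not address.

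The missed visits also cost PK and PASI observations in washout for the pooled PKPD analysis that justified N=45 (14.7). Nothing shows that LOCF values enter that model.

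**What to change.** Leave every stopping criterion unchanged.

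1. Reconcile Protocol 5.1.1, 6.3, 7.8.2, 8.11, 8.12, 12.1.8 and 12.6.1 so that stopping study drug and leaving the study are separate states. Where a passage requires withdrawal from the study for clinical reasons, the sponsor should reconcile it with the others; this point does not ask for that requirement to change.
2. State that a subject who stops study drug, remains in the study and consents keeps the already scheduled PASI, IGA, BSA and PK assessments, timed from Baseline, through Week 28 (at minimum the Week 28 visit), in addition to the SFU Visit.
3. In the SAP, say to which visit a PASI from an SFU at Week 20 or 24 is assigned, and align Protocol 14.5 with SAP 4.2.1.1 on the imputation of the change score.

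The cost is a protocol paragraph with conforming edits and some already planned visits for the subjects concerned. No new procedure is needed. Psoriasis therapy started after stopping must be recorded and considered in the analysis, because it would affect the later PASI values.

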19. Subject has a history of uncompensated heart failure, fluid overload, or myocardial infarction, or evidence of new onset ischemic heart disease or in the opinion of the Investigator other serious cardiac disease, within 12 weeks prior to Baseline.
- 20a. Subject has >2x upper limit of normal (ULN) of any of the following: alanine aminotransferase (ALT), aspartate aminotransferase (AST), alkaline phosphatase (ALP), or >ULN total bilirubin ( $\geq 1.5 \times \text{ULN}$  total bilirubin if known Gilbert's syndrome). If subject has elevations only in total bilirubin that are >ULN and <1.5xULN, fractionate bilirubin to identify possible undiagnosed Gilbert's syndrome (ie, direct bilirubin <35%).

Tests that result in ALT, AST, or ALP up to 25% above the exclusion limit may be repeated once for confirmation during the Screening Period. Upon retesting, subjects whose ALT, AST, or ALP remain above the thresholds defined above, should not be randomized.

For randomized subjects with a baseline result >ULN for ALT, AST, ALP, or total bilirubin, a baseline diagnosis and/or the cause of any clinically meaningful elevation must be understood and recorded in the Case Report form (CRF).

If subject has >ULN ALT, AST, or ALP that does not meet the exclusion limit at screening, repeat the tests, if possible, prior to dosing to ensure there is no further ongoing clinically relevant increase. In case of a clinically relevant increase, inclusion of the subject must be discussed with the Medical Monitor.
21. Subjects with clinically significant laboratory abnormalities (eg, creatinine >1.5xULN, neutropenia <1.5x10^9/L, hemoglobin <8.5g/dL, lymphocytes <1.0 x10^9/L, platelets <100 x10^9/L). Individual screening tests for which the results are in error, borderline, or indeterminate for inclusion in the study, can be repeated once for confirmation during the screening period if they are within 25% of the exclusion limit. Upon retesting, subjects whose results remain outside this threshold should not be randomized.
22. Subjects with any other condition which, in the Investigator's judgment, would make the subject unsuitable for inclusion in the study.
23. Subjects have been exposed to more than 1 biological response modifier (limited to anti-TNF or IL-12/-23) or have received any biologic response modifier during the three months prior to the Baseline Visit. The list of prohibited medications is presented in [Section 7.8.2](#).

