**Table 12–3: Required investigations and follow up for PDILI**

Laboratory value			Immediate		Follow up	
ALT or AST	Total bilirubin	Symptoms a of hepatitis of hypersensitivity	Consultation requirements	Actions	Testing	Evaluation
≥3xULN (and ≥2x baseline) and <5xULN (and ≥2x baseline)	<2xULN	No	
Discussion with Medical Monitor required.
 
Consider need for hepatology consult if there is no evidence of resolution (see Follow up requirements).c
	
Further investigation – immediate IMP discontinuation not required (see Section 12.5.1.2).
 
IMP discontinuation required if any of the following occur:
 
 
• Subject cannot comply with monitoring schedule.
 
• Liver chemistry values continue to increase
 
• Liver chemistry values remain ≥3xULN (and ≥2x baseline) after 2 weeks of monitoring without evidence of resolution
 
	
Essential: Every attempt must be made to have repeat liver chemistry values and additional testing completed within 48 hours at the site with HCP (see Section 12.5.1.4).
	
Monitoring of liver chemistry values at least twice per week for 2 weeks.d
 
 
• Immediate IMP discontinuation required if liver chemistry values continue to increase.
 
 
After 2 weeks of monitoring liver chemistry values:
 
 
• Discontinue IMP if levels remain ≥3xULN (and ≥2x baseline) without evidence of resolutiond
 
 
Continue to monitor until values normalize, stabilize, or return to within baseline values.d

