11.3 Clinical laboratory evaluations

Laboratory data (clinical chemistry, hematology, and urinalysis) and changes from Baseline (if applicable) for numeric variables will be listed by treatment group and visit. Any laboratory variables with values that are BLQ or ALQ will be handled as described in [Section 4.2.2](#) for calculation of changes from Baseline and for summary tables. Values outside the reference range for the numeric variables will be flagged in the listings and in addition, will be listed separately. The reference ranges will also be reported in the listings.

Clinical chemistry and hematology variables will be summarized by treatment group (including All Subjects) at each visit, for both absolute values and changes from Baseline.

Laboratory variables will be grouped according to the laboratory function panel and categorized as normal, high or low, if applicable, based on the reference range supplied by the analytical laboratory. For selected variables that are identified in [Table 11-1](#), the change in category from Baseline will be presented in shift tables at all post-Baseline visits.

The number and percentage of subjects with treatment-emergent markedly abnormal (TEMA) laboratory results (to match the TEAE definition stated in [Section 11.1.3](#)) will be tabulated by treatment group and visit. Markedly abnormal laboratory values will be defined as those categorized as Grade 3 and above based on the ranges defined as per the Common Terminology Criteria for Adverse Events (CTCAE) Version 4.03 (2016). These are provided in [Table 14-4](#). The tabulation will include a category for the incidence of TEMA results over all visits which will also count unscheduled measurements.

In addition, for absolute neutrophil count (ANC), all grade 2 CTCAE abnormalities ($<1.5 - 1.0 \times 10^9/L$) will be listed separately, with results from all visits for any subject that has any grade 2 abnormality.

Laboratory measurements meeting the criteria for TEMA will be listed separately for hematology and chemistry. The listings will include all measurements for any variable with at least one TEMA result for each subject.

Any additional laboratory variables not included in the outputs described previously will be listed separately. These will include the following:

- Serology
- Pregnancy tests (serum and urine)
- Follicle stimulating hormone (FSH) (only for postmenopausal women)

The results of the Quantiferon TB Gold test will be listed separately.

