14.4 Classification of markedly abnormal laboratory values based on CTCAE grades

The criteria for assessing laboratory values as markedly abnormal are presented in [Table 14–4](#).

Table 14–4: Criteria for markedly abnormal laboratory tests

Category	Panel	Variable	Criteria (CTCAE Grade 3 and above)	
Hematology	Red blood cell	Hemoglobin (Decrease)	<80 g/L	
		Hemoglobin (Increase)	>4 g/dL (>40 g/L) above ULN OR >4 g/dL (>40 g/L) above baseline if baseline is >ULN	
	White blood cell	WBC count (Decrease)	<2.0 x 10 ⁹ /L	
		WBC count (Increase)	>100 x 10 ⁹ /L	
	White blood cell differential	ALC (Decrease)	<0.5 x 10 ⁹ /L	
		ALC (Increase)	>20 x 10 ⁹ /L	
		ANC	<1.0 x 10 ⁹ /L	
	Platelet	Platelet	<50 x 10 ⁹ /L	
	Chemistry	Liver function	ALT	>5.0 x ULN
			ALP	>5.0 x ULN
AST			>5.0 x ULN	
Total bilirubin			>3.0 x ULN	
GGT			>5.0 x ULN	
Kidney function		Creatinine	>3.0 x baseline value	
			OR >3.0 x ULN	
		Electrolytes	Calcium (Decrease)	<1.75 mmol/L
			Calcium (Increase)	>3.1 mmol/L
			Magnesium (Decrease)	<0.4 mmol/L
			Magnesium (Increase)	>1.23 mmol/L
			Potassium (Decrease)	<3.0 mmol/L
			Potassium (Increase)	>6.0 mmol/L
Sodium (Decrease)	<130 mmol/L			
	Sodium (Increase)	>155 mmol/L		

Category	Panel	Variable	Criteria (CTCAE Grade 3 and above)
	Lipids	Total cholesterol	>10.34 mmol/L

ULN=upper limit of normal.

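### Six chemistry analytes have no numeric entry limit, yet a Grade 3 value in any of them forces withdrawal from study treatment once the subject has been dosed

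*Protocol*

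**What the plan says.** **Withdrawal.** Criterion 11 in Protocol Section 6.3 begins "Subject has a clinical laboratory value meeting the following criteria". At Grade 3 the rule is immediate: "CTCAE Grade 3 and above: subjects must be withdrawn regardless of relationship to study drug or duration of event". At Grade 2 a transient value is tolerated, but after repeat testing "If this second repeat value is still Grade 2 or above, the subject must be withdrawn". The lead-in to this group of criteria gives the consequence: "Subjects should be withdrawn from all study treatment and will be asked to return for the SFU Visit". Criterion 11 makes no comparison with the value before the first dose.

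**Entry.** Section 6.2, criterion 20a, sets numeric limits for ALT, AST, ALP and total bilirubin. Criterion 21 excludes "Subjects with clinically significant laboratory abnormalities (eg, creatinine >1.5xULN" and then names limits for neutrophils, hemoglobin, lymphocytes and platelets. These are examples in an open list; any other analyte depends on the same judgment. Criterion 22 lets the investigator exclude for any other unsuitable condition. Under Section 6.1, the laboratory results from the Baseline Visit, apart from the pregnancy test, need not be known before dosing.

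**DMC referral.** A sub-bullet of Section 6.4 sends the study to the DMC without delay once a second subject meets any of withdrawal criteria 4, 8a, 9a, 10 or 11. Its parent bullet describes a pattern of adverse events that argues against further dosing.

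**Cut-offs.** SAP Section 14.4, Table 14-4, prints the Grade 3 thresholds. The only Grade 2 range printed is in SAP Section 11.3, which lists "for absolute neutrophil count (ANC), all grade 2 CTCAE abnormalities".

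**The concern.** A mandatory withdrawal threshold should not be one that a subject can already exceed on entry. If it is, the trial can dose someone whom its own rule then removes, for a value that did not change on drug. A subject withdrawn before Week 4 loses one of two active doses in Arm A, or two of three in Arm B, but is still analyzed in the randomized arm (SAP Section 3.6).

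The second worry is the stopping rule. With 45 subjects planned and a trigger of two, one unchanged pre-study value could use up half of a rule meant to detect harm on treatment.

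**Working it through.** **Step 1. Compare entry limits with Grade 3 cut-offs.** Entry limits come from criteria 20a and 21, cut-offs from SAP Table 14-4.

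| Analyte | Excluded at entry | Grade 3 cut-off |
|---|---|---|
| ALT, AST, ALP | >2 x ULN | >5 x ULN |
| Total bilirubin | >ULN (1.5 x ULN or more if known Gilbert's) | >3 x ULN |
| Creatinine | >1.5 x ULN | >3 x ULN, or ">3.0 x baseline value" |
| Neutrophils (10^9/L) | <1.5 | <1.0 |
| Lymphocytes, low (10^9/L) | <1.0 | <0.5 |
| Platelets (10^9/L) | <100 | <50 |
| Hemoglobin, low | <8.5 g/dL (85 g/L) | <80 g/L |
| GGT | none | >5 x ULN |
| Total cholesterol | none | >10.34 mmol/L |
| Sodium (mmol/L) | none | <130 or >155 |
| Potassium (mmol/L) | none | <3.0 or >6.0 |
| Calcium (mmol/L) | none | <1.75 or >3.1 |
| Magnesium (mmol/L) | none | <0.4 or >1.23 |

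Where an entry limit exists, it is stricter than Grade 3, so a subject within it at Screening cannot already be at the absolute Grade 3 level. The six analytes in the lower rows have no such margin, and none of their cut-offs refers to Baseline.

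**Step 2. Count.** Table 14-4 has 11 chemistry analytes, of which 5 have an entry limit: 11 − 5 = 6. Counted as one-sided cut-offs, the table holds 8 (hematology) + 5 (liver) + 1 (creatinine) + 8 (electrolytes) + 1 (cholesterol) = 23.

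- Direct entry limit: 9.
- Indirect limit: 1. Low white cell count is bounded because 1.5 + 1.0 = 2.5, above the cut-off of 2.0.
- High hemoglobin, white cells and lymphocytes: 3, set aside. High hemoglobin already has a Baseline term, and exclusion criterion 12 removes lymphoproliferative disease.
- No entry bound: 23 − 9 − 1 − 3 = 10, or 10/23 = 43% of table rows.

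**Step 3. The two-subject trigger, if such subjects count.** The trigger is 2/45 = 4.4% of planned subjects, or 2/55 = 3.6% with all 10 replacements. Let p be the share of randomized subjects who carry such a value. It is not in the documents, so the values below are assumptions.

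P(at least 2 of 45) = 1 − (1 − p)^45 − 45p(1 − p)^44

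At p = 1%: 1 − 0.636 − 0.289 = 0.075.

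| Assumed p | 0.2% | 0.5% | 1% | 2% |
|---|---|---|---|---|
| P(at least 2 of 45) | 0.4% | 2.2% | 7.5% | 22.7% |

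**Step 4. Effect on the endpoints.** This depends on which visits follow withdrawal.

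- Visits continue off treatment: nothing is carried forward to Week 28.
- The SFU PASI, 20 weeks after the last dose, is placed by date: Week 20 after one dose (28 − 20 = 8 weeks carried) or Week 24 after two (28 − 24 = 4 weeks).
- Only the Early Withdrawal PASI is used, mapped under SAP Section 4.4 to Week 2, 4 or 8: 26, 24 or 20 weeks carried.
- Non-responder imputation at Week 16 applies only if that visit is missing. One lost responder then moves the rate by 1/30 = 3.3 points in Arm A or 1/15 = 6.7 points in Arm B.

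The range of 0 to 26 weeks shows that the documents do not fix an endpoint effect.

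**The case against.** The strongest reply is that judgment at Screening already closes most of the gap. A potassium above 6.0 or a sodium below 130 mmol/L would rarely be called clinically insignificant, and criteria 21 and 22 cover every analyte. That stands. What remains is a value judged unimportant, for which GGT or cholesterol is the plausible case.

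Three stronger readings are tempting, and the documents do not support them.

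- *That such a subject certainly counts toward DMC referral.* The sub-bullet of Section 6.4 names criterion 11 without qualification, but its parent bullet speaks of adverse events. Section 12.1.1 covers what was absent before the initial visit, or recurred or worsened after it. The lead-in to criterion 11 also speaks of events occurring. Read together, these support leaving out an unchanged value. The text is ambiguous, and the outcome is a DMC meeting, not automatic suspension.
- *That absolute thresholds are out of line with the rest of the protocol.* The liver rule does use a Baseline condition, "Liver chemistry values remain ≥3xULN (and ≥2x baseline) after 2 weeks of monitoring without evidence of resolution", but only in the tier where dosing may continue. Its mandatory stop at 5 x ULN is absolute, as is the HADS-D stop at 15. Absolute limits for severe values are a coherent, cautious choice in Phase 2a.
- *That the Grade 2 rule is also defective.* On its wording it could remove a subject with a stable Grade 2 value. But Grade 2 limits for the six analytes are not printed, so this cannot be checked, and relaxing the rule would weaken a deliberate safety stop.

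Table 14-4 is a reporting table that criterion 11 does not cite. It serves here only as the printed source of Grade 3 cut-offs. Section 6.3 also asks sites to contact the Medical Monitor in advance where possible. That helps, but it does not waive a mandatory withdrawal. Criterion 10, by contrast, lets an unrelated Grade 3 adverse event stay with the Medical Monitor's approval.

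**Conclusion.** The mismatch is real but narrow. For six chemistry analytes, a stable pre-study Grade 3 value can pass entry on a judgment of no clinical significance, and the same value must then end study treatment. Nothing elsewhere in the documents exempts it.

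The size is not established. The 43% is a share of table rows, not of subjects, and the trigger probabilities rest entirely on an assumed p. That p must cover a joint event: present before the study, at Grade 3, judged unimportant, and stable. The number of such subjects is probably small. Efficacy is summarized descriptively, the sample size rests on a PKPD model pooled with 240 subjects from PS0010, and up to 10 withdrawn subjects may be replaced, so no threat to the trial's conclusions follows. The case for acting is that the change is cheap and removes an ambiguity in two mandatory rules.

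**What to change.** 1. **Criterion 21.** Add that a Screening value at CTCAE Grade 3 or above, confirmed on the single repeat allowed by Section 6.5, is exclusionary for every analyte to which criterion 11 applies. This only stops the dosing of someone whom the protocol would itself withdraw.
2. **Section 6.4.** State that a laboratory value already at the same grade before the first dose, and not worsened since, is reported to the DMC but does not by itself count toward the two-subject trigger.

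Leave both withdrawal limbs of criterion 11 unchanged. Any exemption for stable Grade 2 values is a clinical trade-off for the sponsor and would need a confirmed pre-dose value.

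**Cost.** Two sentences in an amendment, a comparison with the pre-dose grade when criterion 11 cases are counted, and possibly a few extra screen failures, each 1 of about 90 planned screenings (1.1%). One route stays open: a Grade 3 value first seen in the pre-dose Baseline sample, whose result may arrive after dosing, still leads to withdrawal. Only its count under Section 6.4 changes.
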